### Pharmacokinetic Terms and Definitions

AUC	Area under the concentration-time curve from dosing to infinity
AUC t	Area under the concentration-time curve from dosing up to time t, where t is the last time point at which the concentration is above the lower limit of quantification
% AUC extrap	Percentage of AUC that is due to extrapolation from the last measurable concentration
C max	Maximum concentration observed
CL	Clearance
F	Bioavailability
λ z	First-order rate constant associated with the terminal (log-linear) portion of the concentration-time curve
NCA	Non-compartmental analysis
t 1/2	Terminal elimination half-life
t max	Time of maximum observed concentration (C max )
V z	Distribution volume

## 1 INTRODUCTION

### 1.1 Background

The foot and ankle articular complex must work in concert to enable normal ambulation and movement. In some individuals, either from traumatic injury or due to the degenerative effects of arthritis, motion at one or more of these joints becomes markedly painful, resulting in impaired function and quality of life. When non-operative measures are no longer effective, arthrodesis is an accepted operative treatment option for patients with severe pain or disability caused by arthritis or deformity of the ankle or hindfoot.

Approximately 110,000 foot and ankle arthrodesis were performed in the United States in 2009 and this number is increasing annually because of both an aging population and the continued prevalence of contributory comorbidities. Arthrodesis is designed to relieve pain and restore function associated with the numerous maladies that cause joint destruction, including trauma, diabetes, inflammatory arthritides, seronegative arthropathy, instability, malalignment, and congenital. Although arthrodesis has long been the mainstay of surgical treatment for foot and ankle arthritis, nonunion of the intended fusion construct remains one of the most common complications resulting in morbidity and disability. In fact, there are a number of factors associated with a higher risk for a nonunion result, including: age  $\geq$  60 years, obesity, diabetes mellitus and tobacco product use, etc., which often requires the use of bone grafting to improve fusion rates and, ultimately long-term clinical outcomes.

The biological process involved in bone regeneration requires (i) osteogenic potential that is capable of directly providing cells to the newly forming bone, (ii) osteoinductive factors that are able to cause the osteoblastic differentiation of osteoprogenitor stem cells and (iii) osteoconductive scaffold that facilitate the neovascularization and supports the ingrowth of bone.

Successful fusion surgery must engage the bone regeneration process to produce new bone to bridge the area previously occupied by the joint space and articular cartilage. To enable this process, orthopedic surgeons often will harvest bone, known as autologous bone graft (ABG), from elsewhere in the body to fill the joint.

ABG provides an effective osteoconductive scaffold for new bone formation and contains appropriate growth factors and cells to potentiate new bone formation (osteoinductive). The availability of locally-harvested bone in ankle or foot arthrodesis can be limited, therefore, a second harvest site is often required from either the iliac crest, proximal or distal tibia to facilitate the acquisition of enough bone to support the graft substitute application. Harvesting ABG, however, is associated with both short- and long-term morbidity. Complications of autograft harvest include blood loss, postoperative pain, fracture, infection, other non-infectious wound complications, heterotopic bone formation, hernia, and nerve injury. Baumhauer and colleagues recently

reported the results of a prospective randomized study of patients undergoing ankle and hindfoot fusion procedures using ABG harvested from one of four sites (iliac crest, proximal tibia, distal tibia, and calcaneus). Clinically significant pain at the bone graft harvest site was reported by 35% of patients 3 weeks postoperatively and 18% had persistent pain up to 1 year. A review of the literature suggests that the overall complication rate from tibial graft sites, although it has become a favored source for autograft material for foot and ankle surgery, is 5.5%. These complications range in severity from hematoma/seroma and paresthesia to infection, fracture and invasion of the joint space.

Though advances have been made in improving the safety and efficacy of foot and ankle arthrodesis procedures by utilizing better fixation devices, more recent emphasis has been placed on the biological aspects of bone healing and the development of alternatives that eliminate the need to harvest bone graft to augment fusion. AMPLEX is in development as an alternative to ABG in hindfoot and ankle fusion procedures that require supplemental graft material, including tibiotalar, talocalcaneal, talonavicular and calcaneocuboid fusions. This investigational bone graft substitute is comprised of two parts: 1) bone void filler (BVF) granules made from hydroxyapatite (HA) and beta tricalcium-phosphate ( $\beta$ TCP) that functions as an osteoconductive scaffold and 2) the synthetic peptide B2A that augments local osteodifferentiation. Clinical studies on AMPLEX demonstrated benefit as a bone substitute without the need for a second procedure and the resulting morbidity associated with that second procedure. In a pilot randomized study of 24 subjects comparing AMPLEX to ABG, bone fusion was similar in both groups, and the AMPLEX group demonstrated improvements in bone density, healing and patient functional capacity. No device-related complications were reported.

## 1.2 Scientific Justification for Conducting the Trial

AMPLEX is an investigational medical device supplied in kit form (AMPLEX kit) and must be used as a system. When fully prepared, AMPLEX consists of osteoconductive ceramic granules (BVF) mixed with synthetic B2A peptide. The principal mode of action of the device is based on the osteoconductive granules that act as a scaffold for cellular ingrowth; B2A augments that action. The sterile ceramic granules, supplied by a third party vendor, are currently cleared for use as a BVF for bony voids or gaps of the skeletal system (e.g., extremities, spine and pelvis) that are not intrinsic to the stability of the bony structure. These defects may be surgically- or traumatically-created osseous defects to the bone (K063527, MBCP+).

The primary mode of action of AMPLEX is achieved by the osteoconductive ceramic granules. The granules provide a biocompatible scaffold that enables the migration, proliferation and differentiation of host pre-osteoblast cells, the basis of bone repair. B2A, a synthetic peptide, complements the action of the granules by facilitating osteodifferentiation through its actions on bone morphogenetic protein receptors (BMPRs), augmenting the cell response to local bone morphogenetic proteins (BMPs).

The growth and differentiation of pre-osteoblasts on the ceramic granules is assisted and complemented by B2A in a cooperative process with the native osteoinductive proteins generated as a part of normal bone healing. B2A therefore acts primarily as a selective positive receptor modulator, increasing the sensitivity of cells to natural (endogenous), physiologically-active levels of BMP-2, and thereby augmenting osteodifferentiation. The augmentation of osteodifferentiation can only occur, however, when B2A and BMP-2 are each above their respective biological threshold levels. This only occurs at the implant site where the B2A-coated granules are located and where BMP-2 is up-regulated as a part of the normal bone healing process. Over time, the scaffold is naturally resorbed by the body, leaving only the newly formed bone in its place.

The control material used in this study, ABG, is harvested from a location other than the graft site, for example, the calcaneus, proximal tibia, distal tibia or iliac crest, and administered by standard surgical procedure. The selection of the ABG harvest site is at the discretion of the surgeon and based on medical judgment. The harvested bone is cleaned of soft tissue and morselized in standard fashion.

### **1.3 Benefit / Risk Aspects**

Arthrodesis remains the most common surgical procedure for patients with debilitating ankle and hindfoot arthritis. Average nonunion rates remain high (10-15%) but can be substantially higher in patients with co-morbid factors such as diabetes and other metabolic diseases, obesity, smoking, age  $\geq 65$  and osteoporosis. The data with both ABG and bone graft replacement products, particularly in light of their nearly ubiquitous use in this setting and the apparent equivalence of their fusion rates, suggest that a major differentiator is the lack of pain, dysfunction and morbidity related to graft donor sites when bone graft replacement products are utilized.

The inclusion of patient reported outcomes, functional evaluations and quality of life assessments is therefore important in evaluating the differences between these approaches. The current clinical trial was designed with this in mind, incorporating both radiologic assessment of fusion rate and validated scales to assess pain and functional outcome.

### **1.4 Clinical Benefit**

The proposed clinical study is designed to demonstrate that AMPLEX is non-inferior to ABG for bone fusion in a population indicated for single, double, or triple hindfoot arthrodesis or ankle arthrodesis surgery with supplemental graft material. The potential benefit to AMPLEX subjects is successful fusion of the ankle or hindfoot via an operation that is smaller in magnitude and devoid of the risks and additional pain associated with the harvesting of autogenous bone graft. Subjects who receive AMPLEX may experience the following potential benefits:

1. Similar rate of fusion compared to autograft without the additional risks of the autograft procedure (i.e., harvest site pain, longer anesthetic and longer procedure, harvest site infection, harvest site fracture, or other complications)
2. Higher rate of fusion compared to autograft without the additional risks of the autograft procedure
3. Similar or higher rate of fusion at earlier time points than autograft without the additional risks of the autograft procedure
4. Similar or larger extent of fusion as measured by trabecular bridging of bone across the fusion site.

### 1.5 Analysis of Increased Risks to Treatment Subjects

Pre-clinical testing and pilot studies conducted outside the United States indicate that AMPLEX should be safe and effective. However, until this is proven in a prospective, randomized clinical trial utilizing a concurrent control group comprised of subjects undergoing ankle or hindfoot fusions, subjects receiving AMPLEX may experience increased risk of:

1. Allergic reaction (local or systemic response)
2. Ectopic bone growth (bone forming outside of normal bone growth areas)
3. Abnormal cell growth (growth of tissue or cells beyond the norm)
4. Negative effects on pregnancy or fetus
5. Immune response (bodily response against foreign material)
6. Significant increase in liver enzyme measures

Table 1. Below describes these increased risks to treatment subjects and their mitigation. Additional descriptions of procedure and study related risks are provided in [Appendix 1](#), Anticipated Adverse Events.

**Table 1 Risks: Description & Mitigation**

Risks	Description/Mitigation
Allergic reaction (local or systemic response)	Biocompatibility testing has been performed on the AMPLEX material demonstrating a minimal reactivity.  Monitoring of study conduct and safety data will be conducted on an ongoing basis by Sponsor and Data Monitoring Committee, governed by a Charter. If these groups identify any new or unforeseen risks they will notify the Sponsor and render an opinion on potential study modifications/stopping.
Ectopic bone growth (bone forming outside	Osteoconductive materials, including allograft bone, have a risk of ectopic bone growth. The preclinical battery of in-

of normal bone growth areas)
	
vitro and in-vivo animal testing performed on AMPLEX has not identified any instances of exuberant bone growth. It has also not been seen in any of the feasibility clinical cases.
 
Monitoring of study conduct and safety data will be conducted on an ongoing basis by Sponsor and Data Safety Monitoring Committee, governed by a Charter. Evidence of this would be detectable on the CT scans used to evaluate efficacy. If these groups identify any new or unforeseen risks they will notify the Sponsor and render an opinion on potential study modifications/stopping.

Abnormal cell growth (growth of tissue or cells beyond the norm)
	
An extensive preclinical battery of in vitro and in vivo animal testing of AMPLEX and PREFIX did not identify an impact on tumor cell growth, tumor promotion, or metastatic behavior, thus minimizing the potential for such an event to occur with the treatment device. The study enrollment criteria include an exclusion for subjects with a prior history of active malignancy with the exclusion of basal cell carcinoma of the skin.
 
Monitoring of study conduct and safety data will be conducted on an ongoing basis by Sponsor and Data Monitoring Committee, governed by a Charter. If these groups identify any new or unforeseen risks they will notify the Sponsor and render an opinion on potential study modifications/stopping.


Negative effects on pregnancy or fetus
	
The preclinical testing has projected that the B2A component of AMPLEX is completely eliminated within six weeks of implantation and during that time that circulating B2A levels are quite low. Therefore, the risk of an effect on a fetus is unlikely.
 
However, to avoid this potential risk, female subjects are excluded from the trial if they are pregnant or lactating, or intend to become pregnant during the course of this study.
 
Monitoring of study conduct and safety data will be conducted on an ongoing basis by Sponsor and Data Monitoring Committee, governed by a Charter. If these groups identify any new or unforeseen risks they will notify the Sponsor and render an opinion on potential study modifications/stopping.

Immune response (bodily response against foreign material)
	
Pre-clinical and clinical immunogenicity testing during PREFIX and AMPLEX development have not demonstrated any immune reactions nor development of significant anti-B2A antibody formation.

	
Although remote, based on the established data, this risk is mitigated through single exposure to AMPLEX and the protocol specified assessment of antibody response.
 
Despite this being a remote risk, monitoring of study conduct and safety data will be conducted on an ongoing basis by Sponsor and Data Monitoring Committee, governed by a Charter. If these groups identify any new or unforeseen risks they will notify the Sponsor and render an opinion on potential study modifications/stopping

Elevated liver enzymes (from the B2A peptide)	
Transient excursions in lab values, specifically liver function enzymes, have been noted in the pilot clinical studies conducted in both the treatment and control groups. After extensive consultation with various experts, it was determined that these elevations are largely related to surgery itself, concomitant medications and pre-existing conditions.
 
Despite this being a remote risk, monitoring of study conduct and safety data will be conducted on an ongoing basis by Sponsor and Data Monitoring Committee (DMC), governed by a Charter. If these groups identify any new or unforeseen risks they will notify the Sponsor and render an opinion on potential study modifications/stopping.

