### **3.4.4 Trial Population**

Subjects will be  $\geq 18$  and  $< 75$  years of age and candidates for tibiotalar (ankle) arthrodesis or single, double, or triple hindfoot (talocalcaneal-, calcaneocuboid- or talonavicular-joint) arthrodesis with supplemental graft material. Subjects shall be screened prior to randomization to ensure they meet inclusion/exclusion criteria. The screening will include a review of all imaging and critical comorbid risk factors for nonunion by the Investigator.

A Pharmacokinetic (PK) assessment will be conducted in a sub-set of subjects to assess the amount of B2A in blood (plasma) after surgery, on Days 1, 2, 4, 7, and 15, and will include a baseline, pre-procedure evaluation. The sub-set of subjects will include up to approximately 30 AMPLEX subjects, allowing pharmacokinetic evaluation in at least 20 AMPLEX subjects. Both genders will be represented. Blood samples will be collected and processed to plasma for laboratory evaluation (plasma B2A concentration).

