## 4 SELECTION OF TRIAL POPULATION

### 4.1 Trial Population

#### 4.1.1 Inclusion Criteria

Subjects enrolled in the study must meet the following inclusion criteria:

1. Signed written informed consent
2. Male or female at least 18 years of age but less than age 75
3. Indicated for ankle or hindfoot arthrodesis and require one of the following arthrodesis procedures:
  - Tibiotalar (ankle)
  - Talocalcaneal (subtalar)
  - Talonavicular
  - Calcaneocuboid
  - Double hindfoot (e.g., talonavicular and talocalcaneal joints)
  - Triple hindfoot (subtalar, talonavicular and calcaneocuboid joints)
4. Presents with pain on weight-bearing of at least 40 mm on a 100 mm VAS at the area indicated for arthrodesis
5. Presents with at least one comorbid risk factor (based on Baumhauer *et al* 2013) that warrant the use of supplemental autogenous bone or allograft
  - Radiographic evidence of bone defect, deficit, subsidence or subchondral cyst
  - More than one joint to be fused
  - Involvement of other adjacent or nonadjacent joints
  - Large surface area
  - Intra-articular or extra-articular deformity
  - Post-traumatic arthritis
  - Diagnosis of osteoporosis
6. The Investigator determines the joint space(s) can be adequately filled with graft material (AMPLEX or ABG) according to the following parameters:
  - Single hindfoot joint fusion: up to 5 cm^3
  - Double or triple hindfoot fusion: each individual joint up to 5 cm^3, but overall, not more than 10 cm^3 for the full complement of joints
  - Ankle fusion: up to 10 cm^3
7. Each fused joint can be rigidly stabilized with at least 1 and no more than 3 screws across the fusion plane. (Supplemental pins and staples may be used, as well as supplemental screws and plates external to the fusion site(s).)
8. Willing and able to comply with all study requirements including all postoperative clinical and radiographic evaluations
9. For women of childbearing potential (not post-menopausal for 12 months or surgically sterile), a urine pregnancy test with a negative result must be obtained at screening and within 24 hours prior to procedure. These trial participants must commit to adequate birth control (e.g., oral contraceptive, two methods of barrier birth control, or abstinence) through the 78 week follow-up

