#### **4.2.2 Randomization**

Once written informed consent is obtained and eligibility is confirmed the subject can be randomized. Randomization must occur prior to surgery, with a recommendation to take place on the day of surgery or as close to the procedure as possible. Subjects will not be made aware of their randomization result prior to surgery.

Subjects will be randomly assigned on a two to one (2:1) basis to either the treatment group (AMPLEX) or the control group (ABG). Randomization will be stratified by clinical center, surgical site (hindfoot vs. ankle), and nonunion risk factors (none vs. any of: obesity, diabetes, previous hindfoot/ankle surgery, or smoking history). Permuted block randomization will be performed within strata. To minimize the opportunity for the sequence to be predicted, the block size will be variable. The randomization schedules for all strata will be generated in advance by an independent statistician who is not going to be involved in the study conduct using a computerized random number generator. Investigational sites will not have access to the randomization schedules.

Administration of randomization assignments will be accomplished using an electronic system. The study coordinator or a designee will obtain the randomization assignment per the provided randomization instructions. A copy of the randomization assignment will be maintained in the subject's file.

If, between the time of randomization and the beginning of surgery, the subject becomes ineligible or withdraws, the reason for failure to treat will be recorded in the subject's study records.

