### **5.5 Treatment Compliance**

#### **5.5.1 Dispensing and Accountability**

AMPLEX will only be dispensed to subjects who meet the eligibility criteria and are randomized to the treatment group in the trial. The Investigator (or his/her designated personnel, e.g. trial nurse) will maintain a device accountability log/form(s) detailing the dates and quantities of the investigational devices dispensed to, and used by, each subject, as well as the batch numbers. The monitor will verify the device accountability during the trial.

Access to investigational devices shall be controlled and the investigational devices shall be used only in the clinical investigation and according to the protocol. The Sponsor shall keep records to document the physical location of all investigational devices from shipment of investigational devices to the investigation sites until return or disposal. The principal Investigator or an authorized designee shall keep records documenting the receipt, use, return and disposal of the investigational devices, which shall include:

- date of receipt
- identification of each investigational device (kit lot number)
- expiry date, if applicable
- date or dates of use

- subject identification
- date on which the investigational device was returned/explanted from subject, if applicable
- date of return of unused, expired or malfunctioning investigational devices, if applicable
- date and manner of device destruction

All study (investigational) device accountability records will be maintained by the Investigator or qualified designee, stored in a secure location and reviewed during monitoring visits by the assigned CRA/monitor.

If AMPLEX is prepared, but not implanted or used for whatever reason, it will be discarded per the institution's policy and the circumstances recorded in the device accountability log/form(s). If needed (e.g., due to faulty preparation, accidental contamination, etc.), and with time permitting, a new device may be prepared according to the same randomization treatment assignment, (e.g., any given subject will be assigned a single randomization code/assignment).

At the end of the study or as frequently as deemed appropriate, all unused study (investigational) device kits should be returned to the Sponsor or its designated representative unless otherwise instructed.

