### 6.1.2 Screening/Pre-Operative Visit

The potential risks and benefits associated with participation in the study will be explained to potential study subjects. Written informed consent must be obtained before the subject can begin any study-specific procedures that are not standard of care (e.g. immunology sample collection). In addition, if governing laws require, all subjects must sign the appropriate authorization for use, collection, and disclosure of protected health information and receive a copy of their signed informed consent.

The following assessments/activities will be performed at the screening or pre-operative visit:

- Obtain informed consent and authorization to disclose and release protected health information as applicable
- Medical History:
  - Record medical history
  - Record all concomitant medications taken within the past month, including vitamins/supplements such as glucosamine and chondroitin, and pain relief medication including those that are herbal
  - Record comorbidities
- Physical Assessment:
  - Verify inclusion/ exclusion criteria
  - Record vital signs, weight, height and BMI
  - Collect standing A/P, lateral and oblique X-rays of the hindfoot or ankle (historical X-rays, taken up to 24 weeks prior to the planned date of surgery, will also be accepted)
  - Collect urine sample(s) for pregnancy test from female subjects of childbearing potential, for standard urinalysis and for microscopic urinalysis (only if required)
  - Collect four blood samples for: 1) non-fasting chemistry (including aspartate aminotransferase [AST], alanine aminotransferase [ALT], alkaline phosphatase [APT], gamma-glutamyl transferase [GGT] bilirubin and hemaglobin [HbA1c]), 2) hematology, 3) immunogenicity testing for B2A antibodies, and 4) immunological testing (hepatitis B virus [HBV], hepatitis C virus [HCV], human immunodeficiency virus [HIV]). Additional details for the collection and handling of blood samples are provided in the SRM
  - Review with the subject the instructions for, and ask the subject to complete, the FAAM-ADL Questionnaire and the weight-bearing pain VAS
  - Review the instructions for and ask the subject to complete the SF-12 Questionnaire

- Investigator Screening Assessment:
  - Review medical history and comorbidities
  - Record patient-reported VAS pain on weight-bearing at site where fusion is to be performed

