### 6.1.3 Day of Surgery

Once eligibility is confirmed the subject can be randomized, but the subject will not be notified of randomization result until after the surgery.

The following assessments/activities will be performed on the day of surgery:

- Verify subject meets eligibility criteria
- Record date and time of hospital admission
- Record medical history and comorbidities since screening
- Record vital signs
- Identify the arthrodesis site(s) / index joint(s)
- Collect urine sample for pregnancy test from female subjects of childbearing potential (within 24 hours prior to procedure)
- Record volume of blood loss and blood use during surgery
- Record the number and type of screws and screw systems used during surgery
- Record operation start and end time (incision to closure)
- Measure and record the volume of AMPLEX implanted per joint and identify the joint; and record the amount remaining after surgery. For ABG, record the volume harvested for treatment, implanted per joint, identify the joint, and record the amount remaining after surgery.
- Perform specific intraoperative data collection
- Record any protocol deviations
- Record all concomitant medications including (anesthesia) taken since the screening visit
- Record any AEs experienced from time of screening

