## 7 TRIAL ASSESSMENTS

### 7.1 Schedule of Assessments

**Table 3 Schedule of Assessments**

Visit number	Screening	Treatment	Follow-up					
	V1	V2 Procedure	V3	V4	V5	V6	V7	V8
Weeks	-12	-	2	6	12	24	52	78
Days	Days -84 to -1	Day 1	Day 15 (+/- 3)	Day 43 (+/- 14)	Day 85 (+/- 14)	Day 169 (+/- 30)	Day 365 (+/- 30)	Day 547 (+/- 30)
Informed consent	X							
Medical History/ comorbidities	X	X						
Supplemental graft requirement confirmation	X							
Eligibility criteria verification	X	X						
Physical assessment of foot/hindfoot, vital signs	X	X	X	X	X	X	X	X
Pregnancy test [1] (if applicable)	X	X						
Standard Urinalysis [2]	X							
Clin. labs: chemistry and hematology [3]	X		X	X	X			
Immunological Testing for HBV, HCV and HIV	X							
Serum for B2A Ab testing [4]	X			X	X			
Identification of target arthrodesis site	X	X						
Subject randomization [5]		X						
Arthrodesis procedure		X						
Specific intraoperative data collection [6]		X						
Graft material volumes		X						
A/P, lateral and oblique X-rays of hindfoot/ankle	X†	X [7]		X	X	X	X	X
Foot and ankle CT scan					X	X	X	
FAAM-ADL	X				X	X	X	
Weight bearing pain at fusion site VAS	X				X	X	X	
Graft Harvest site pain VAS			X	X	X	X	X	
SF-12	X					X	X	
Adverse event evaluation [8]		X	X	X	X	X	X	X
Concomitant Medications	X	X	X	X	X	X	X	X

† At the screening/pre-operative visit, A/P, oblique and lateral X-rays will be collected (historical X-rays taken up to 24 weeks prior to the planned date of surgery will also be accepted).  
 [1] Pregnancy test may be performed within 24 hours of the procedure  
 [2] If positive for blood, leukocytes, or nitrite, microscopic urinalysis will be performed.  
 [3] HbA1c is to be performed at screening for all subjects  
 [4] B2A Antibody testing may continue past the 12 week follow-up visit if there is a positive test at 12 weeks.

[5] The subject will be randomized as close to the time of surgery as possible, with the recommendation that the randomization be performed on the day of the surgical procedure.  
 [6] See Section 6.1.4 referencing the Surgical Manual.  
 [7] Perform immediately following surgery or within 1 week following the procedure.  
 [8] Collected from time of informed consent. Post-treatment outcomes that are evaluated as efficacy endpoints, such as pain on weight-bearing, harvest site pain, etc. will not be reported as AEs.

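### Protocol Table 1 says lactating women are excluded, but no numbered eligibility criterion contains that exclusion

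*Protocol*

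**What the plan says.** Section 1.5, Table 1, lists possible added risks of AMPLEX and how each is reduced. In the row on harm to a pregnancy or fetus, it says that preclinical work projects complete elimination of B2A within six weeks, with low circulating levels meanwhile, and calls an effect on a fetus unlikely. To avoid the risk all the same, it states that "female subjects are excluded from the trial if they are pregnant or lactating", and it adds women who plan a pregnancy during the study.

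In the numbered lists, inclusion 9 is the only criterion on reproductive status. Section 4.1.1 words it as "For women of childbearing potential (not post-menopausal for 12 months or surgically sterile), a urine pregnancy test with a negative result must be obtained". The first test falls at the screening visit and the second shortly before surgery, and the woman must also commit to birth control through week 78. The synopsis version differs only in the timing of the second test. Exclusions 1 to 27 mention neither pregnancy nor lactation.

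The protocol ties entry and treatment to these lists:

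- Section 3.4.4: "Subjects shall be screened prior to randomization to ensure they meet inclusion/exclusion criteria".
- Section 4.2.2: "Once written informed consent is obtained and eligibility is confirmed the subject can be randomized".
- Section 5.5.1: "AMPLEX will only be dispensed to subjects who meet the eligibility criteria"; assignment to that arm is the other condition.
- Section 6.1.3, day of surgery: "Verify subject meets eligibility criteria".

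**The concern.** Table 1 presents the exclusion of lactating women as a safeguard already in place, and ethics boards and regulators reading the risk section would take it as such. A site decides eligibility from the numbered criteria, and lactation is not among them. If a site works from the list alone, the safeguard is not applied. Because no numbered criterion is broken, the enrollment need not be recorded as an eligibility deviation, so the lapse could pass unnoticed. What is at stake is whether a protection the protocol claims is actually given. No statistical result depends on it.

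**Working it through.** No formula applies and the plan states no figure on this point. The check sets the texts side by side.

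**1. Where lactation is mentioned.** A search of both documents for lactation, breast-feeding or nursing a child finds one mention, in Table 1.

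**2. The numbered criteria.** There are 9 inclusion + 27 exclusion = 36 criteria, in Section 4.1 and again in the synopsis. The number naming lactation is 0.

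**3. Table 1's enrollment restrictions against the lists.**

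| Restriction in Table 1 | Numbered criterion |
|---|---|
| History of malignancy, basal cell skin cancer excepted | Exclusion 18 |
| Pregnant | Inclusion 9, negative urine test |
| Planning a pregnancy | Inclusion 9, in substance, through the birth-control commitment |
| Lactating | None |

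The other three restrictions have a counterpart; lactation alone has none.

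**4. Whether another criterion reaches it indirectly.**

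- Inclusion 9: a pregnancy test does not detect lactation, and birth control does not bear on it. The criterion also does not apply to a surgically sterile woman, who may be lactating.
- Exclusion 11: it covers medical conditions or circumstances that the investigator believes should prevent participation. It could be used for lactation, but it is discretionary, whereas Table 1 states a fixed bar.
- Medical history, taken at screening and updated on the day of surgery: it might bring lactation to light, but no criterion then tells the site to exclude the woman.

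**5. Following a case through.** Take a lactating woman who is otherwise eligible. If she is of childbearing potential, tests negative twice and uses contraception, inclusion 9 is met. If she is surgically sterile, it does not apply. No exclusion names her condition. She passes the checks in Sections 3.4.4, 4.2.2 and 6.1.3, and if randomized to AMPLEX she may receive it under Section 5.5.1. Table 1 says she is excluded. The two parts of the protocol give different answers for the same woman.

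**6. Effect on the analysis.** The mITT set in SAP Section 6.2 takes every randomized subject whose surgery is started, so she would be counted either way. The per-protocol exclusions named in SAP Section 5 concern conditions or procedures that could affect fusion or its assessment, and neither document links lactation to fusion. The sample size, margin and error rates do not involve eligibility wording.

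**The case against.** The best reply is that Table 1 is itself protocol text, stated as fact, and Section 14.4 requires the trial to follow the approved protocol. A site that knowingly enrolled a lactating woman would contradict it. That is right, and it narrows the problem to a site overlooking a sentence in the background section. It does not remove the problem, because the working checks point to the criteria lists.

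A second reply is that Table 1 may be the part in error. Its row concerns the fetus, and it gives no reason for including lactation. Neither the risk list in Section 1.5 nor the study-product events in Appendix 1 names a risk to a nursing infant. The documents do not settle which text is wrong, so the fix has to allow both directions.

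Three stronger readings are tempting, and the documents do not support them:

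- *That the lack of a lactation step or schedule row is a further defect.* Many exclusions have none of their own, for example prisoner status, litigation, recent trial participation and prior BMP exposure (exclusions 22, 23, 24 and 26). They are applied through the general eligibility checks at screening and on the day of surgery. The only thing missing is a line in the list.
- *That the hepatitis and HIV rule has the same fault because it too is absent from the list.* Section 7.3.3.2 already makes negative serology at Visit 1 a condition of entry, so that rule operates as written.
- *That infants are shown to be at risk.* The protocol describes no such risk and calls circulating B2A low.

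**Conclusion.** The inconsistency is real and the point is minor. Table 1 states a fixed exclusion that none of the 36 numbered criteria contains, and those criteria decide randomization and the dispensing of AMPLEX. The cover from exclusion 11 and the medical history is partial and discretionary.

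Few subjects are likely to be affected; that is a judgement, since the documents give no count. There is no effect on power, type I error or the analysis sets. The matter is a stated safeguard not carried into the list, and no harm has been shown.

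The conclusion rests on the protocol and SAP alone. The consent pages, eCRF and Site Reference Manual were not available, and any of them may raise lactation. A reader might infer that lactating women will in practice be enrolled; the documents do not establish that. Even if those materials do cover lactation, Table 1 and Section 4.1 would still disagree.

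**What to change.** At the next amendment, add 'Currently lactating' as a numbered exclusion in Section 4.1.2 and in the synopsis. The existing eligibility verification at screening (Section 6.1.2) and on the day of surgery (Section 6.1.3) will then apply it, with no new test, visit or schedule row. If the sponsor does not intend the exclusion, remove the word from Table 1 instead, so that the risk section claims only what the criteria deliver.

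The cost is one line of text in two places. Section 14.4 requires ethics approval of an amendment before use, across up to 50 centers in two countries, so it should travel with the next amendment. Adding the line turns away only women whom Table 1 already says are excluded.
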